7.1.2 Mycophenolate Mofetil/ Mycophenolic Acid

All enrolled subjects will be on MMF/MPA at the time of study entry at a minimum dose of 1000 mg/720 mg per day. Once subjects are enrolled in the study, doses may be adjusted at the discretion of the study investigator for gastrointestinal intolerance, cytopenias, infections or other conditions that require dose adjustment. All mycophenolate prescribers in the study will be required to enroll in the FDA mycophenolate REMS (risk evaluation and mitigation strategy) program.

7.1.3 Prednisone

Use of corticosteroids is not prohibited in this trial. However, subjects requiring use of corticosteroids >10 mg per day for treatment of long-term conditions (e.g., lupus) will not be enrolled.

7.1.4 Other Immunosuppressive Medications

Subjects requiring the use of cyclosporine and/or azathioprine will not be enrolled in this study.

7.2. Anti-Infective Prophylactic Medications

Anti-infective prophylaxis medications will be per standard of care at each clinical center.

7.3. Prohibited Medications

7.3.1. Non-Leukoreduced Blood Products

For subjects requiring treatment, leukoreduced blood products should be used whenever possible.

7.3.2. Vaccinations

The use of live vaccines will be proscribed during trial participation, as per standard of care for kidney transplant recipients. Examples include (but are not limited to) the following: intranasal influenza, measles, mumps, rubella, oral polio, BCG, yellow fever, varicella, and TY21a typhoid vaccines.

Subjects should not receive any vaccination (live or inactivated) within 14 days prior to blood collection for Treg manufacturing and 28 days after the date of Treg infusion. These requirements are in place to minimize the chance of having enrichment of vaccine specific Tregs in the product and ensure that Treg infusion does not negatively impact immunity elicited by the vaccine.

7.3.3. Medication Interactions

Grapefruit and grapefruit juice inhibit cytochrome P450 3A4 and P-gp activity and should therefore be avoided with concomitant use of EVR. Patients with rare hereditary problems of galactose intolerance, the Lapp lactase deficiency or glucose-galactose mal absorption should not take EVR as this may result in diarrhea and malabsorption.

Administration of medications known to interact with tacrolimus and/or EVR is allowed but tacrolimus and EVR levels should be carefully monitored and dosing titrated to maintain the target levels to minimize toxicity while maintaining efficacy.

7.4. Treatment of Rejection

Patients who are clinically suspected to have a rejection will undergo a kidney biopsy. Biopsies will be read locally according to the Banff criteria and if acute rejection is diagnosed, it will be treated according to the current standard of care. Samples of blood, urine and kidney tissue will be obtained for mechanistic analysis prior to the treatment. Digital images of the biopsies will also be reviewed later by the central pathology core.

8. Study Mandated Procedures

8.1. Blood Draws

Blood draws are necessary after kidney transplantation to monitor allograft function. Whenever possible, study participants will have additional blood drawn for research purposes at time points when standard of care testing is done. Some blood tests will be performed at the local hospital laboratory. Blood for mechanistic assays described in this protocol will also be collected and shipped to core laboratories.

A blood collection of 450-500 mls will be drawn for Treg isolation and manufacture for subjects with hematocrit 30% or higher once the subject is determined to be eligible and randomized to Group 2. Blood collection for this purpose can be repeated once, if necessary, for manufacture of the Treg product (see 8.2 Leukapheresis).

8.2. Leukapheresis

Subjects with hematocrit less than 30% will have leukapheresis performed for PBMC collection. Subjects with hematocrit greater than 30% may undergo leukapheresis or have whole blood collection. The study team will make a decision in the best interest of a particular subject based on the current clinical picture.

8.3. Kidney Biopsy

Study participants will undergo surveillance biopsies as standard of care between 3 and 7 months after transplantation and approximately one year after transplantation. Research specimens will be collected during these procedures and digital images will be sent to the central pathologist for scoring. The biopsy obtained 3-7 months after transplantation will be used to determine study eligibility and local read will be confirmed by central pathologist. The one-year biopsy will fall 7 months after study group assignment and will be used to assess the efficacy endpoint. The one-year biopsy and all for-cause biopsies will be reviewed by the central pathologist.

Additionally, a protocol kidney biopsy will be performed 2 weeks after polyTreg infusion (Group 2). This biopsy is for research purposes only and will be used for mechanistic assays and to confirm eligibility for mTOR conversion. This biopsy will be reviewed by the central pathologist.

9. Known and Potential Risks and Benefits to Participants

9.1. Risks of PolyTregs

Although Treg infusion has been innocuous in animal models, there is currently scant experience in humans. Three Treg therapy trials in GvHD have been reported. The first-in-man trial by Trzonkowski et al involved two patients (Trzonkowski, 2009). The first patient had chronic GvHD two years after transplantation. After receiving $0.1 \times 10^6/\text{Kg}$ flow sorted ex vivo expanded Tregs from the donor, the symptoms subsided, and the patient was successfully withdrawn from IS. The second patient had acute GvHD disease that progressed despite three infusions with an accumulative dose of $3 \times 10^6/\text{Kg}$ expanded donor Tregs. A larger scale phase I trial led by Brunstein et al (Brunstein, 2010) enrolled twenty- three patients with advanced hematologic malignancy. The patients were treated with two units of umbilical cord blood as source of stem cells and effector T cells. Tregs were isolated using anti-CD25 immunomagnetic bead selection from third-party cord blood samples that had 4 to 6 HLA match with the recipient. Up to $6 \times 10^6/\text{Kg}$ Tregs were infused after ex vivo expansion using anti-CD3 and anti-CD28 conjugated beads. The infused Tregs were detectable in circulation for up to 7 days. During the one-year period after Treg infusion, the investigators observed no DLTs and AEs when compared to historical controls. Incidences of acute and chronic GvHD were reduced in patients received Treg therapy. The third trial enrolled 28 patients with high-risk hematological malignancies (Di Ianni, 2011). Patients received anti-CD25 immunomagnetic bead enriched donor Tregs without ex vivo expansion four days before receiving one haplo-mismatched hematopoietic stem cell and Tconv transplants from the same donors. A majority of the patients received $2 \times 10^6/\text{Kg}$ Tregs with $1 \times 10^6/\text{Kg}$ Tconv and no adjunct IS was given after transplant. Patients demonstrated accelerated immune reconstitution, reduced CMV reactivation, low incidence of tumor relapse and GvHD. Collectively, these studies show that Treg therapy has minimal toxicity in the setting of GvHD.

Recently, a phase I/II study applying polyclonally expanded FACS purified Tregs to type diabetic patients has been reported by the Trzonkowski group (Marek-Trzonkowska N, 2012). The study enrolled 10 type 1 diabetic children (aged 8-16 years) within 2 months after diagnosis. Four patients received 10×10^6 Tregs/kg body wt and the remaining 6 patients received 20×10^6 Tregs/kg body weight. The patients were followed for 4-5 months after Treg infusion, and no toxicity of the therapy was noted. The authors concluded that Treg therapy was safe and well tolerated in children.

A phase I Treg dose-escalating trial evaluating safety of Treg therapy in type 1 diabetic patients completed enrollment and infusion in October 2013. Fourteen enrolled subjects received a single infusion of Tregs. Three subjects were treated in each of the first and second dosing cohorts with 0.05×10^8 and 0.4×10^8 cells, respectively, and four subjects were treated in the third dosing cohort with 3.2×10^8 cells. Notably, three of the subjects in cohort 3 and 4 were enrolled at treated at Yale (New Haven, Connecticut). As of August 2014, 115 adverse events had been reported in 15 subjects since the beginning of the trial. All 14 treated subjects have reported at least 1 adverse event. One subject who underwent phlebotomy but was withdrawn before treated reported 1 adverse event before withdrawal from the trial. Seventy-one events were judged as mild in severity, 35 were judged as moderate, and nine were judged as severe. Four events were judged to be serious. Thirty events were judged to be possibly related, 21 unlikely related and 64 unrelated to study therapy. There were no grade 4 or 5 adverse events. Four serious adverse events (SAE) have been reported since the beginning of the trial. Three severe (grade 3) hypoglycemic SAEs, one judged unlikely related and two judged unrelated to the investigational product have been reported. One severe (grade 3) hyperglycemic SAE judged unrelated to the investigational product has been reported.

9.1.1. Potential Risks of Treg Administration

T cell suppression

Tregs are known to suppress naïve T cell responses to a variety of antigens. Less is known about ongoing immune responses especially to viruses and bacteria. It is not known whether Tregs will alter protective immunity. Only recipients with current immunizations including TdAP, pneumococcal and seasonal influenza vaccines will be enrolled in the study. During the flu season, seasonal influenza vaccine will be administered prior to the qualifying biopsy for all transplant recipients and at least 28 days prior to Treg isolation. Subjects immune to hepatitis B can be enrolled in the study; or if non-immune/ HBV naïve, can be enrolled only if their kidney donor has negative HB core antibody and negative HB surface antigen.

Infusion reaction

Side effects reported from previous human trials involving T cell infusions include transient fever, chills, and/or nausea. Subjects will be pre-medicated with acetaminophen 650 mg by mouth and diphenhydramine hydrochloride 25-50 mg by mouth or IV, prior to the infusion of Tregs. These medications may be repeated every six hours as needed. Patients will not receive systemic corticosteroids such as hydrocortisone, prednisone, prednisolone (Solu-Medrol) or dexamethasone (Decadron) at any time, except in the case of a life-threatening emergency, since this may have an adverse effect on T cells. If corticosteroids are required for an acute infusion reaction, an initial dose of hydrocortisone 100 mg may be used.

Infection

As with any therapy that suppresses the immune system, there is a risk of developing infections. It should be noted that on a theoretical basis, this risk is minimal, since the total input of Tregs is approximately 3-5% of the endogenous resident Treg population. We will perform plasma CMV DNA quantitative PCR in all recipients prior to enrollment and exclude those who are positive. Study subjects will be monitored for CMV reactivation by plasma CMV DNA quantitative PCR.

Lymphoproliferative disease

Treg immunosuppression has been shown to enhance tumor growth in some small animal model systems. Thus, complications such as lymphoproliferative disease are possible on a theoretical basis. Clinical experience in transplant recipients suggests that the risk of lymphoproliferative disease is highest in those who develop a primary EBV infection while immunosuppressed. Thus, individuals without prior exposure to EBV are excluded from this study unless the kidney donor is EBV naive. In previously exposed individuals, EBV reactivation is associated with a degree of immunosuppression higher than that likely to be observed in this study since the total input of Tregs is approximately 3-5% of the endogenous resident Treg population. Furthermore, the previously observed rate of PTLD in kidney recipients is relatively low at 0.68% (Smith JM, 2006). Nonetheless, careful attention will be paid to the potential for this complication and we will perform EBV quantitative DNA PCR to screen patients prior to enrollment and monitor for reactivation during the study.

Loss of tumor surveillance

T lymphocytes are one major component of tumor surveillance, and it is possible that cells that inhibit T lymphocytes could impair this function. There has not been evidence of tumors in preclinical models. Nonetheless, the long term follow up of all treated patients will determine whether there is evidence of an increase in the frequency of tumors.

Reproductive risks

There may be an unexpected risk to an unborn or nursing child. Pregnant and breastfeeding women will be excluded from participation in the study. Females must have a negative pregnancy test prior to enrolling in the study. Female participants must agree to not participate in a conception process (e.g., active attempt to become pregnant or in vitro

fertilization) for up to one year after Treg dosing. Females must agree to use a reliable and effective form of birth control for two years after Treg dosing. This includes oral contraceptives, barrier methods, or abstinence. Female subjects will also be required to undergo a urine pregnancy test prior to cell administration. A positive pregnancy test will result in holding of scheduled cell administration.

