Further, it has been shown that conversion from a CNI to an mTOR inhibitor in transplant recipients is associated with an increase in Treg number and activity (Carroll RP, 2013) (Gallon L T. O.-R., 2015). Animal studies of tolerance induction using Treg infusions have shown prolonged survival of infused Tregs (Singh K, 2014) and graft acceptance with concomitant sirolimus therapy (Ma A, 2011) (Ma A Q. S., 2009). Therefore, as an added strategy to improve the survival of the infused Tregs, we propose to convert the maintenance immunosuppression from a CNI-based regimen to an everolimus-based regimen in eligible subjects who have safely received polyTregs infusions and have demonstrated a reduction in inflammation on their follow up biopsies at 2 weeks. The previous experiences at UCSF in patients with type 1 diabetes mellitus as well as in a pilot study involving kidney transplant recipients found that infused Tregs reach a peak in the circulation at 2 weeks post-infusion and are still detectable in the circulation at 6 months and 1 year. In animal models, trafficking of infused Tregs in inflamed tissue and draining lymph nodes can be seen within a few hours after infusion. The reduction of inflammatory cell load can be detected in three days, but is typically more pronounced 1 to 2 weeks after the Treg infusion (Lee K, 2014) (Mahne AE, 2015). This delay is likely because Tregs need to accumulate, become activated, and proliferate locally before exerting their suppressive effects. In the clinical setting when we cannot frequently sample the graft, we think it is most likely that we will observe an improvement in graft inflammation at 2 weeks and this will be our signal to initiate a conversion from a CNI to everolimus. Previous studies in kidney transplant recipients have adequately demonstrated the safety of conversion from CNI to everolimus at > 6 months post-transplant (Budde K & Investigators., 2012) (Chhabra D, 2013).

3. Study Design

[figure not shown]

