3.3. Secondary Safety Endpoints

3.3.1. Secondary Safety Endpoints

The safety of PolyTregs (Group 2) will be described in comparison with CNI-based maintenance IS therapy (Group 1) by:

1. Timing, incidence, and severity of polyTregs infusion reaction
2. Timing, incidence, and severity of culture-proven and clinically diagnosed infection after PolyTreg infusion
3. Timing, incidence, and severity of acute rejection using Banff grading
4. Timing and incidence of BK viremia and CMV reactivation
5. Timing and incidence of > 10% decrease in eGFR compared to baseline

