10.4. Follow Up Visits

Group 2 participants will have study visits on day 1, 7, 14, 28, 84, 182, and 364 after Treg infusion. Participants in Group 1 will have the same visits in parallel with Group 2 patients, starting 48 days after study group assignment. Please refer to Appendix 2 for Group 1 schedule of events and Appendix 3 for Group 2 schedule of events.

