10.6. Visit Windows

Study visits should take place within the time limits specified below (Table 2). The designated visit windows for each scheduled visit are also indicated on the Schedules of Events.

Table 2. Visit Windows	
Study Visit	Visit Window
Study Eligibility Biopsy	5 months \pm 8 weeks
Study Eligibility/ Study Group Allocation	\leq 2 weeks after qualifying biopsy
Group 1 Only	
Day 41/ Visit T0-G1	\pm 3 days
Day 48/ Visit 1	\pm 5 days
Day 55/ Visit 2	
Day 69/ Visit 3	
Day 125/ Visit 4	
Day 223/ Visit 5	\pm 14 days
Day 405/ Visit 6	
Group 2	
PBMC Collection Visit T-16	Dictated by infusion date and manufacturing timeline.
Treg Infusion Day / Visit T0	Infusion can occur any time up to and including day 62 after central pathology confirmation.
Visit T1 / Day 1	\pm 1 hour (Group 2)
Visit 1 / Day 7	\pm 1 day
Visit 2 / Day 14	\pm 3 days
Visit 3 / Day 28	
Visit 4 / Day 84	
Visit 5 / Day 182	\pm 14 days
Visit 6 / Day 364	\pm 14 days

11. Mechanistic Assays

The goal of the mechanistic studies in this trial is to evaluate the impact of polyTregs on the immunological profiles of kidney transplant recipients. We will accomplish this by determining: 1) impact of Treg infusion on the numbers of circulating and graft-infiltrating Tregs; 2) impact of Treg infusion on the inflammation in the graft; 3) impact of Treg infusion on the peripheral blood biomarkers of rejection and graft injury.

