11.1.2. Detection of Infused Tregs in Graft Using Deuterium Labeling (Deu-biopsy)

Tregs have a propensity to traffic to and accumulate in sites of inflammation. Since patients in this trial are selected to have inflammation in the kidney allograft, the infused Tregs may infiltrate the graft. To determine if this occurs, fresh biopsy samples (1/2 to a full 16G core) will be collected 2 weeks after Treg infusion. The tissue will be digested to dissociate the cells into single cell suspension. Infiltrating CD45⁺immune cells and its various subsets will be isolated using FACS and the level of ²H enrichment among the purified cells will be determined as described above for blood samples.

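### CMV reactivation is compared between arms, but Group 2 appears to have fewer scheduled CMV PCR tests than Group 1, with none at the infusion day or Day 7

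*Protocol*

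**What the plan says.** Section 9.1.1 of the protocol names infection as a potential risk of Treg administration and answers it with surveillance: "Study subjects will be monitored for CMV reactivation by plasma CMV DNA quantitative PCR". It gives no frequency; that is left to the schedules of events. Section 3.3.1 lists "Timing and incidence of BK viremia and CMV reactivation" among the outcomes described for Group 2 in comparison with Group 1. Protocol Table 7 analyses CMV incidence in mITT1, which holds both arms.

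SAP section 8.2.1 goes further. It compares incidence between groups by Fisher's exact or Cochran-Mantel-Haenszel test, and time of event by ANOVA, Kruskal-Wallis or t-test, with follow-up to 405 days after allocation. SAP section 7.1.2 says that, in general, data enter the analysis whatever the time of assessment. Nothing limits the CMV comparison to visits at which both arms are tested.

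On visits, section 10.4 of the protocol states: "Group 2 participants will have study visits on day 1, 7, 14, 28, 84, 182, and 364 after Treg infusion". It continues: "Participants in Group 1 will have the same visits in parallel with Group 2 patients, starting 48 days after study group assignment".

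**The concern.** Reactivation found by PCR is seen only if a test falls while virus is present. When one arm is tested more often, its detected incidence rises and its events are dated earlier, even if the true risk is the same. Here the arm that appears to be tested less is the treated arm, and the gap lies in the first weeks after infusion. Section 2.4.3 says of that period that "infused Tregs reach a peak in the circulation at 2 weeks post-infusion". The bias would make polyTregs look safer on a risk that the protocol itself names. Section 10.4 presents the visits as parallel, so a reader of the results would have no reason to suspect unequal testing.

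**Working it through.** The documents state no number of CMV tests, so there is no figure to reproduce. The check is a count, followed by a detection calculation.

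**1. Group 1 tests (Appendix 2).** After screening, the CMV/EBV PCR row is marked at Days 41, 48, 55, 69, 125, 223 and 405, and at a clinically indicated biopsy: 8 marks, 7 of them scheduled. Section 10.6 labels the first "Day 41/ Visit T0-G1". Subtracting 41 gives days 0, 7, 14, 28, 84, 182 and 364, which are the infusion day and the Group 2 visits other than Day 1. Six scheduled tests therefore fall after the index day.

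**2. Group 2 tests (Appendix 3).** The same row shows 5 marks after screening. In that table, basic chemistry shows 8 and begins three columns earlier. In Appendix 2, chemistry and CMV PCR begin together at Day 41 with 8 marks each.

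**3. Which Group 2 days are these?** The text copy of Appendix 3 is misaligned, so two readings are possible.
- *Printed column heads taken literally:* Days 28, 84, 182, 364 and clinically indicated biopsy, so 4 scheduled tests.
- *Columns anchored to the text:* section 11.1.2 says that "fresh biopsy samples (1/2 to a full 16G core) will be collected 2 weeks after Treg infusion", yet that row's only mark stands in the column where the CMV marks begin, printed as Day 28. On this anchor the first CMV test is Day 14. There are then 4 scheduled tests, or 5 if a column has been lost.

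On either reading no mark falls at the infusion day or Day 7. The like-for-like count after the index day is 6 against 4 or 5.

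**4. Chance of detection.** Assume equal true risk, onset *s* uniform over days 0 to 28 after the index day, and viremia lasting *d* days. Then

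P(detected) = share of *s* in (0, 28] for which some test day *t* satisfies *s* ≤ *t* ≤ *s* + *d*.

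Test days up to Day 28 are 7, 14 and 28 in Group 1 (the Day 0 test catches none of these onsets). In Group 2 they are 14 and 28, or 28 only. For *d* = 7:
- Group 1 catches onsets in 0–7, 7–14 and 21–28: 21/28 = 75%.
- Group 2, first test Day 14, catches 7–14 and 21–28: 14/28 = 50%.
- Group 2, first test Day 28, catches 21–28: 7/28 = 25%.

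| Length of viremia (assumed) | Group 1 | Group 2, first test Day 14 | Group 2, first test Day 28 |
|---|---|---|---|
| 7 days | 75% | 50% | 25% |
| 14 days | 100% | 100% | 50% |
| 21 days | 100% | 100% | 75% |
| 28 days | 100% | 100% | 100% |

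**5. Timing.** Take viremia that persists until found, with onset uniform over days 0 to 14. The mean delay from onset to the first positive scheduled test is 7/2 = 3.5 days in Group 1. In Group 2 it is 14 − 7 = 7 days (first test Day 14) or 28 − 7 = 21 days (first test Day 28). Timing is thus affected even where incidence is not.

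**6. Effect on the test.** With 7 per arm, Fisher's exact two-sided p is 0.070 for 4/7 against 0/7 and 0.021 for 5/7 against 0/7. A plausible detection gap is unlikely to change significance; it distorts the reported proportions and times.

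**The case against.** A reader who takes the printed column heads at face value might infer that Group 2 has only four CMV tests against seven, with none in the first four weeks, so that early viremia on polyTregs is missed. The documents do not support that.

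- The two-week biopsy row places Day 14 in the column where the CMV marks begin.
- In the graft gene-expression row, only one column separates the two-week biopsy from what must be the Day 182 biopsy, although Days 28 and 84 both lie between. A column appears to have collapsed.
- The kSORT row has the same five marks as CMV in Group 2, but six in Group 1 starting at Day 55, the Day 14 counterpart. The CMV row may have lost a mark too, so 5 against 8 is not secure. A broken table is not a fault of the plan.
- Even read literally, Day 28 is a test at four weeks. Longer episodes are caught in both arms, and clinically indicated testing and adverse event reports also contribute.
- Seven for Group 1 includes the index day, whose Group 2 counterpart precedes infusion. Section 11.4 banks Group 2 plasma and serum on that day and names CMV as a possible later test.
- SAP section 7.1.4 calls the analysis primarily descriptive.

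All of this stands and reduces the point. It does not remove it: no Group 2 mark appears at the infusion day or Day 7 on either reading, and the SAP has no rule for unequal testing. If Group 2 is in fact tested at Day 14, the incidence gap is confined to episodes shorter than 14 days.

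**Conclusion.** The point holds in a limited form. Incidence and timing of CMV reactivation are compared between arms on all available data, while Group 2 appears to be tested less often soon after infusion. The likely bias favours polyTregs.

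For a 7-day viremia the detection gap is 75% against 50% or 25%, depending on whether the first Group 2 test is Day 14 or Day 28. For a 14-day viremia it is nil or 100% against 50%. At 28 days there is none. These figures assume equal true risk, uniform onset over 28 days, and episode lengths that the documents do not give. They also depend on a table whose columns must be checked in the original. The documents do not establish that the first month after infusion goes unobserved. With 7 per arm, the harm is mainly to the descriptive proportions and times.

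**What to change.** 1. Confirm the Group 2 CMV PCR row in the original Appendix 3, in particular whether Day 14 is marked.
2. State in SAP section 8.2.1 that the between-arm comparison of CMV incidence and timing uses only tests scheduled in both arms, plus clinically indicated tests, with time counted from infusion in Group 2 and from Day 41 in Group 1. Define the matched visits from the confirmed row. Fixing Group 2 at Days 28, 84, 182 and 364 now could discard a Day 14 result in the treated arm.
3. Report the unmatched Group 1 tests separately: Days 41 and 48, and Day 55 only if Group 2 has no Day 14 test.
4. Optionally, test the banked Group 2 infusion-day plasma to match Day 41. That sample precedes infusion, so it shows status at the index day, not an event after treatment.

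The cost is one check of the source table and a sentence or two in the SAP. The downside is that a few early Group 1 detections leave the formal comparison. The gain is mainly fairer descriptive proportions and times.
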